**Randomized Trial of Patient-Reported Outcome Measurement in Heart Failure Clinic
(PRO-HF Trial)**

Version 5

June 30, 2023

CLINICAL TRIAL SUMMARY

Title	Randomized Trial of Patient-Reported Outcome Measurement in Heart Failure Clinic
Study Objectives	
Primary objective is to evaluate the impact of routine assessment of patient-reported health status among outpatients with heart failure on heart failure health status one year later.
 
Secondary objectives include evaluating the following:
 
 - Changes in heart failure therapy patterns - Changes in healthcare utilization (testing, clinic visits, acute care visits) - Patient experience - Concordance between clinician and patient perception of patient health status
Study Design	
This randomized clinical trial evaluates the routine assessment of patient-reported health status, using the Kansas City Cardiomyopathy Questionnaire-12 (KCCQ-12) among adult outpatients with heart failure. Any patients being seen in the heart failure clinics are eligible for enrollment. Patients will be enrolled via secure email or telephone call. They will be randomized in a 1:1 fashion to KCCQ-12 assessment or usual care with permuted block randomization stratified by clinician. Participants randomized to KCCQ-12 assessment will complete the KCCQ-12 at every heart failure clinic visit. Their results will be available to clinicians to assist with clinical management. Health status surveys will not be integrated into clinical care for patients in the usual care arm.
 
In a subset of the total study, we will compare clinician perception of patient health status and patient experience across the two arms.

Number of Participants	Minimum of 1,200 participants will be randomized; 600 patients in sub-study
Trial Location	Stanford Hospital & Clinics adult heart failure clinic
Inclusion Criteria	Adult heart failure clinic visit
Exclusion Criteria	None
Intervention	Participants randomized to KCCQ assessment will complete a KCCQ-12 survey with each heart failure clinic visit. These responses will be shared with their heart failure clinician. Treating clinicians will continue to make all diagnostic and treatment decisions at their discretions.

Primary Endpoint	KCCQ-12 score at least 1 year post-randomization

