6.3 Randomization

We will randomize patients using a secure online randomization module on REDCap. Randomization will be stratified by treating clinician with a block sizes of 2 and 4. Randomization occurs automatically via the online platform after a patient consents. Following randomization, the patient either receives the usual care KCCQ survey via REDCap or notification of an upcoming KCCQ survey via MyHealth for those in the KCCQ arm.

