9. STATISTICAL CONSIDERATIONS AND ANALYSIS PLAN

9.1 Primary Analysis and Statistical Power

The primary effectiveness outcome is the difference in KCCQ-12 overall summary score after one year of follow-up. Scores will be compared using mixed effects linear regression with adjustment for baseline KCCQ-12 score and a random intercept for the treating clinician. The primary analysis will be limited to patients with follow-up scores. Baseline covariate adjustment can substantially improve the precision of the statistical estimate. This has been previously shown to improve statistical power even in randomized trials with baseline covariate balance (as modeled below in the statistical power analysis).¹⁻³ The covariate used for adjustment of the primary analysis (baseline KCCQ) has been selected due to the moderate association with follow-up health status. As a secondary analysis, we will repeat the analysis with adjustment for other baseline characteristics (age and left ventricular ejection fraction) that have also been previously shown to be associated with health status.⁴⁻⁶ As an additional secondary analysis, the unadjusted KCCQ-12 scores will be compared using a two-sample t-test.

Prior work has suggested a 6 point increase in the KCCQ represents a small improvement and 11 a moderate improvement, with a standard deviation of 24.⁷⁻⁹ However, these estimates represent a significant change for an individual. A smaller mean change across a population may be clinically meaningful. The sample size calculations are based on prior Stanford Heart Failure clinic data. Prior studies of populations with heart failure have found an average KCCQ score of approximately 67. With 1,200 patients, with 20% loss to follow-up, we estimate a 97% power to detect a difference of 6, a 90% power of a mean difference of 5 in the KCCQ-12, and 73% power for a mean difference of 4 in the KCCQ-12.

As discussed above, the statistical power should be amplified with baseline covariate adjustment. We assumed baseline KCCQ-12 would explain approximately 35% of the variance in the final KCCQ-12. With baseline adjustment, we estimate approximately 55% power for a mean difference of 3 in the KCCQ-12 and 81% power for a mean difference of 4. This was estimated by simulating trial results.

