Secondary outcomes will include evaluating the effect of KCCQ assessment on heart failure therapy use and healthcare resource utilization. Details regarding each outcomes are listed above in the “Study Outcomes” section. Each secondary outcome will be evaluated using multivariable regression with adjustment for prespecified patient characteristics: age, left ventricular ejection fraction, baseline therapy/utilization, and Charlson Comorbidity Index. A standard regression model will be selected based on the distribution of the outcome. Therapy use (a binary outcome) will be evaluated using multivariable logistic regression. Therapy doses (ordinal outcome) will be evaluated using an ordinal regression model (including no therapy as the base category). The number of medication changes each visit (a count outcome with a high frequency of no medication changes) will be evaluated using a zero-inflated negative binomial model. Hospitalizations and telephone encounters will also be evaluated using a zero-inflated negative binomial model. Clinic visits (count outcomes without a high frequency of zero events) will be evaluated using a standard negative binomial model. For each model, an indicator variable for allocation to the KCCQ assessment arm will be included. The coefficient on this variable represents the effect of PRO collection. Each model will be adjusted for the baseline rate (e.g. hospitalizations or telephone encounters in the prior year) or baseline treatment (e.g. baseline therapies and doses) to improve model precision. Each of the secondary outcomes will be analyzed for the subgroup with a history of heart failure/cardiomopathy and a baseline KCCQ-12 score of <100. For secondary outcomes of treatment intensity (clinic visits, therapy rates, and testing), we will also evaluate if the association between baseline KCCQ-12 and the secondary outcome is significantly larger in the KCCQ arm than the usual care arm.

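### The therapy and utilization models and the supporting t-test leave out the clinician, the stratification factor, and so give away a little power

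*Combined protocol and SAP*

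**What the plan says.** Section 6.3 sets the design: "Randomization will be stratified by treating clinician with a block sizes of 2 and 4". The summary adds the ratio: "They will be randomized in a 1:1 fashion to KCCQ-12 assessment or usual care". Patients, not clinicians, are the units randomized.

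The analysis follows that design in most places. A clinician random intercept is specified for the primary KCCQ-12 model and for the domain and clinical summary score models (Section 9.1), and for the ordinal models of clinic experience and concordance (Sections 9.3.1 and 9.3.2).

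It is absent in two places:

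- **Section 9.1, additional secondary analysis:** "the unadjusted KCCQ-12 scores will be compared using a two-sample t-test".
- **Section 9.2, Secondary Outcomes:** "Each secondary outcome will be evaluated using multivariable regression with adjustment for prespecified patient characteristics: age, left ventricular ejection fraction, baseline therapy/utilization", with the Charlson index completing the list. The models named are logistic, ordinal, negative binomial and zero-inflated negative binomial. The clinician is not mentioned for any of them, and no reason is given.

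**The concern.** Permuted blocks within clinician make the arms nearly balanced on clinician. Differences between clinicians therefore contribute almost nothing to the true sampling error of the arm comparison. An analysis that ignores the clinician still counts those differences as noise, so it claims less precision than the design delivers.

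Section 9.1 itself argues for covariate adjustment on grounds of precision and power, even when the arms are balanced. The same reasoning applies to the stratification factor.

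At stake is some power for the named secondary endpoints (therapy use and dose, testing, visits, calls, admissions). Treating clinicians keep full discretion over diagnosis and treatment, so these endpoints could plausibly vary by clinician, though the documents do not say by how much. There is also an inconsistency: the KCCQ and sub-study ordinal models respect the stratification and these do not.

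**Working it through.** **Inputs from the plan.** Section 9.1 gives the sample and loss, "With 1,200 patients, with 20% loss to follow-up, we estimate a 97% power to detect a difference of 6", so 1,200 × 0.80 / 2 = 480 per arm. It gives the spread, "with a standard deviation of 24", and the remaining targets, "a 90% power of a mean difference of 5 in the KCCQ-12, and 73% power for a mean difference of 4 in the KCCQ-12".

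**Assumed.** Two-sided alpha of 0.05, which is not stated but reproduces the plan's power. Share of outcome variance due to clinician (ICC) from 0 to 0.10, because the plan gives none. Twelve clinicians in the simulations.

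**Step 1: the plan's own figures.** The t-test SE is 24 × √(2/480) = 1.549. Power is Φ(δ/SE − 1.96), which gives 97.2%, 89.8% and 73.3% for 6, 5 and 4 points. The stated 97%, 90% and 73% are reproduced, with no clinician term.

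**Step 2: the t-test with and without the clinician.** If the arms are balanced within clinician, the true SE is 1.549 × √(1 − ICC), and the t-test SE is too wide by the factor 1/√(1 − ICC).

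- Power with clinician: Φ(δ/[1.549√(1 − ICC)] − 1.96)
- Actual power of the t-test: Φ((δ/1.549 − 1.96)/√(1 − ICC))
- Actual type I error of the t-test: 2Φ(−1.96/√(1 − ICC))

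For a 4-point difference at ICC 0.10: 4/1.549 = 2.582; (2.582 − 1.96)/0.949 = 0.656, so the t-test has 74.4% power. With clinician, 4/1.470 − 1.96 = 0.76, so power is 77.7%. Type I error is 2Φ(−2.066) = 0.039.

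| ICC (assumed) | SE with clinician | t-test SE too wide by | t-test type I error | t-test power | Power with clinician |
|---|---|---|---|---|---|
| 0 | 1.549 | 0% | 0.050 | 73.3% | 73.3% |
| 0.01 | 1.541 | 0.5% | 0.049 | 73.4% | 73.7% |
| 0.02 | 1.534 | 1.0% | 0.048 | 73.5% | 74.2% |
| 0.05 | 1.510 | 2.6% | 0.044 | 73.8% | 75.5% |
| 0.10 | 1.470 | 5.4% | 0.039 | 74.4% | 77.7% |

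**Step 3: simulation of the linear case.** 4,000 runs per setting, blocks of 2 and 4 within clinician, 20% random loss. At ICC 0.10 with no effect, the t-test's mean SE was 1.542 against an empirical 1.483, with 4.6% rejections. With clinician in the model it was 1.471 against 1.473, with 5.1%. Power for 4 points was 73.9% without and 76.9% with clinician. The formula treats balance within clinician as exact. Random loss disturbs it slightly, so the t-test's empirical SE lies a little above 1.470, and the table is best read as an upper bound at each ICC.

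**Step 4: a logistic check.** 1,200 patients, no loss, no other covariates, log odds ratio 0.35, 800 runs per setting.

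| Clinician SD (logit) | Estimate without → with | Printed SE without → with | Power without → with |
|---|---|---|---|
| 0 | 0.352 → 0.355 | 0.117 → 0.117 | 84.3% → 84.4% |
| 0.45 | 0.337 → 0.355 | 0.117 → 0.120 | 81.0% → 81.9% |
| 0.60 | 0.326 → 0.354 | 0.117 → 0.122 | 82.0% → 84.0% |

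The printed SE rises and the estimate moves away from the null; the gain appears as power. Monte Carlo error of one power figure is √(0.82 × 0.18/800) = 1.4 points. Both models were fitted to the same data, so the differences are better determined than that, but they remain only indicative. Under no effect at SD 0.45 and 0.60, rejection was 4.3% and 5.0% without clinician and 4.6% and 5.6% with it, so any conservatism is too small to see here.

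**The case against.** The t-test is deliberately crude. It supports a primary model that already contains the clinician, and no primary conclusion rests on it. By the plan's own figures for 4 points (73% unadjusted, 81% with baseline score), omitting baseline KCCQ-12 costs it more than omitting the clinician. This stands, and it is why keeping the t-test with a label is acceptable.

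For the Section 9.2 models, adjustment for each patient's own baseline therapy or utilization may already absorb part of a stable clinician effect. This also stands: the remaining gain is unknown and could be small. It does not explain why the stratification factor is left out there and kept elsewhere.

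Three stronger readings are tempting, and the documents support none of them:

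- **Ignoring the clinician inflates false positives**, as it would in a cluster-randomized trial. Here patients are randomized within clinician, so the error runs the other way.
- **All secondary analyses omit the clinician.** The domain and clinical summary score analyses and the sub-study ordinal models include it.
- **Intervals are too wide for every therapy and utilization endpoint.** The factor 1/√(1 − ICC) belongs to the linear comparison. In the logistic check, adding the clinician widened the printed interval on the log-odds scale.

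**Conclusion.** The omission is real, conservative in direction and small. The primary analysis is unaffected. For the KCCQ-12 t-test, the clinician term is worth about 0.7, 1.7 or 3.3 points of power for a 4-point difference at an assumed ICC of 0.02, 0.05 or 0.10, and nothing at ICC 0. These figures rest on 480 per arm, SD 24, two-sided 0.05 and near-balance within clinician.

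The firmer part of the point is the set of therapy and utilization models in Section 9.2, where no comparable supporting role explains the omission. The size of the gain there cannot be established from the documents. The logistic check suggests 1 to 2 points of power under its assumptions; ordinal and count models were not simulated. This is a worthwhile tidy-up, not a threat to validity.

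**What to change.** - **Section 9.2, Secondary Outcomes:** add a clinician term, as a random intercept or fixed effect, to each model. For the zero-inflated negative binomial models, place it in the count part and prespecify a fallback if the model does not converge. State that the odds ratios from the logistic and ordinal models are then conditional on clinician.
- **Section 9.1:** keep the two-sample t-test as a crude check labelled as conservative under stratified randomization, or replace it with the mixed model containing arm and clinician intercept only.

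The clinician is already recorded as the randomization stratum, so no new data are needed. The cost is revised SAP text, somewhat more model-fitting work (mainly for the zero-inflated models), and a conditional rather than marginal odds ratio to explain in the report.

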Secondary Endpoints	
Treatment patterns at 12 months:
 
 • Rates of guideline-directed therapy use • Dose of guideline-directed medical therapy • Advanced heart failure therapy evaluation • Cardiovascular testing 
Healthcare resource use at 12 months:
 
 • Heart failure clinic visits (in-person and televisits) • Heart failure telephone encounters (other than visits) • Emergency department visits • Hospitalizations (heart failure and non-heart failure)
Other Outcomes of Interest in Sub-Study	
 • Clinician perception of health status • Patient experience
Assessment Schedule	
 • Baseline KCCQ-12 at time of first clinic visit • Repeat KCCQ-12 within 12-15 months post-randomization 
Sub-study:
 
 • Patient experience survey • Clinician evaluation of patient health status
Study Duration	Patients will be enrolled for 12 months. Expected follow-up will be 12-15 months post-randomization. Patients will be followed until their first clinic visit after one year. Patients without a follow-up visit within 15 months, will be contacted for final outcome ascertainment at that time.
Statistical Considerations	A sample size of 1,200 randomized participants has 95% power to detect a mean difference in KCCQ-12 of 5 between arms (72 in KCCQ arm versus 67 in usual care; SD ~24) and an 80% power to detect a mean difference in KCCQ-12 of 4 without covariate adjustment.

TABLE OF CONTENTS

1. LIST OF ABBREVIATIONS AND DEFINITONS	5
2. BACKGROUND AND RATIONALE	6
3. HYPOTHESIS	8
4. STUDY OBJECTIVES	9
5. STUDY DESIGN	10
6. STUDY PROCEDURES	13
7. TREATMENT ARMS	17
8. STUDY ASSESSMENT AND SCHEDULE	18
9. STATISTICAL CONSIDERATIONS AND ANALYSIS PLAN	19
10. DATA HANDLING AND RECORD KEEPING	23
11. DATA AND SAFETY	24
12. PROTOCOL AMENDMENTS	25
13. REFERENCES	26
14. APPENDICES	27

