6.2 Enrollment and Enrollment

Patients with a heart failure clinic appointment during the 6-month enrollment period will be contacted regarding potential enrollment approximately one week before their visit via secure email. The email will include information regarding the study and consent. There will also be contact information for additional information. Patients who consent will be randomized to KCCQ assessment or usual care. Patients who decline enrollment will receive no further contact from the study team.

Patients without an email response (confirming or declining participation) will be contacted via postal letter approximately two weeks before their clinic visit with information about the study and the opportunity to either enroll in the trial or decline further communication. Patients who neither decline or enroll will be contacted by telephone a few days before the visit. They have the ability to consent or decline further communication during the telephone encounter. Individuals who do not respond via telephone may also be contacted via text message.

We aim to enroll at least 1,200 patients over the 6 month enrollment period. If we enroll 1,200 patients prior to 6 months, we will still complete the 6-month enrollment period with a potential enrollment exceeding 1,200 patients given the minimal-risk nature of the study and ability to provide more precise effect estimates. If the trial fails to enroll 1,200 patients by 6 months, we will discuss reducing the trial enrollment versus extending enrollment with the IRB and the National Institute of Health (the trial sponsor).

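### Power: the synopsis figures leave out the planned 20% loss, and the adjusted powers in section 9.1 do not follow from the stated 35% explained variance

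*Combined protocol and SAP*

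**What the plan says.** The synopsis (Clinical Trial Summary, Statistical Considerations) states: "A sample size of 1,200 randomized participants has 95% power to detect a mean difference in KCCQ-12 of 5 between arms". It gives means of 72 and 67 and an SD of about 24, and adds "80% power to detect a mean difference in KCCQ-12 of 4 without covariate adjustment". It does not mention loss to follow-up next to these figures.

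Section 9.1 uses the same 1,200 patients and an SD of 24 but allows for loss: "With 1,200 patients, with 20% loss to follow-up, we estimate a 97% power to detect a difference of 6, a 90% power" for a difference of 5, and 73% for a difference of 4. It also restricts the analysis set: "The primary analysis will be limited to patients with follow-up scores".

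Section 9.1 then turns to the baseline-adjusted primary model. The assumption is "We assumed baseline KCCQ-12 would explain approximately 35% of the variance in the final KCCQ-12". The result is "we estimate approximately 55% power for a mean difference of 3 in the KCCQ-12 and 81% power for a mean difference of 4". The only account of the method is "This was estimated by simulating trial results".

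Section 6.2 makes 1,200 a minimum: "We aim to enroll at least 1,200 patients over the 6 month enrollment period".

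**The concern.** The synopsis and section 9.1 give different unadjusted powers for one design: 95% against 90% for a difference of 5, and 80% against 73% for a difference of 4. The synopsis carries the more favourable pair. Within section 9.1, adjusting for a covariate that explains 35% of the variance should raise power by more than the plan reports. For a difference of 4 the plan moves only from 73% to 81%.

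At stake is how the precision of the primary model is read. Section 9.1 argues that mean differences smaller than the individual-level threshold of 6 may matter. The difference detectable with 80% power is about 3.5 points if 35% is the explained variance, but about 4.1 if 0.35 is really the correlation. That affects how a null result would be interpreted. It also affects what is carried into the multicenter trial for which section 2 says this study will supply preliminary data.

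**Working it through.** **Inputs**
- 1,200 randomized 1:1, so 600 per arm (synopsis).
- SD 24 (synopsis and section 9.1).
- 20% loss, so 0.8 × 600 = 480 per arm analysed (section 9.1).
- Explained variance R² = 0.35 (section 9.1).
- Two-sided 5%. This is not stated with the power figures; it is inferred because it reproduces section 9.1 below.

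**Formula.** SE = SD × √(2/n), with n per arm, and power ≈ Φ(d/SE − 1.96). The noncentral t agrees within 0.1 point. For the adjusted model, SD is replaced by SD × √(1 − R²).

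**Step 1: reproduce section 9.1, unadjusted.** SE = 24 × √(2/480) = 1.549.

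| Difference | d/SE | Power | Section 9.1 |
|---|---|---|---|
| 6 | 3.873 | 97.2% | 97% |
| 5 | 3.227 | 89.7% | 90% |
| 4 | 2.582 | 73.3% | 73% |

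All three match, which supports SD 24, 480 per arm and two-sided 5%. A two-sided alpha of 0.025 would give 94.9%, 83.8% and 63.3%.

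**Step 2: synopsis, unadjusted.** With no loss, SE = 24 × √(2/600) = 1.386.

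| Difference | Power at 600 per arm | Power at 480 per arm | Synopsis |
|---|---|---|---|
| 5 | 95.0% | 89.7% | 95% |
| 4 | 82.3% | 73.3% | 80% |

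Required n per arm is 2 × [24 × (1.96 + z)/d]². For 95% at 5 (z = 1.645) this is 599, which is essentially everyone. For 80% at 4 (z = 0.842) it is 565, or about 6% loss. The 80% may simply be 82.3% rounded down. Neither figure is compatible with 20% loss.

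**Step 3: adjusted, as stated.** Adjusted SD = 24 × √0.65 = 19.35 and SE = 19.35 × √(2/480) = 1.249.
- Difference 3: d/SE = 2.402, power 67.1% (stated 55%, gap 12 points).
- Difference 4: d/SE = 3.203, power 89.3% (stated 81%, gap 8 points).

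Simulated ANCOVA trials with 480 analysed per arm and no clinician effect (an assumption) gave 66.2% and 89.4% over 10,000 trials each. A second set of 4,000 each gave 67.4% and 89.4%. Clipping scores to the 0–100 range gave 65.6% and 87.4%.

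**Step 4: what could produce 55% and 81%?**

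| Setting (480 per arm and SD 24 unless noted) | Power for 3 | Power for 4 |
|---|---|---|
| R² = 0.30 | 63.9% | 87.0% |
| R² = 0.40 | 70.5% | 91.5% |
| R² = 0.15 | 55.6% | 80.0% |
| Correlation 0.35 (R² = 0.1225) | 54.3% | 78.7% |
| Change score, correlation √0.35, SD 21.69 | 57.2% | 81.5% |
| R² = 0.35, two-sided alpha 0.025 | 56.4% | 83.2% |
| R² = 0.35, SD 27 | 56.9% | 81.2% |
| R² = 0.35, 370 per arm | 55.9% | 80.3% |
| R² = 0.35, 600 per arm (no loss) | 76.6% | 94.7% |

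At SD 24 and 480 per arm, 55% for a difference of 3 solves to R² of about 0.14, and 81% for a difference of 4 to about 0.17. Reading the 35% as anything from 0.30 to 0.40 does not close the gap.

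**Step 5: difference detectable with 80% power at 480 per arm.** This is (1.96 + 0.842) × SE: 3.50 at R² = 0.35, 4.07 at correlation 0.35, and 4.34 unadjusted.

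**The case against.** The strongest reply is that no reader is led to expect more power for the primary analysis than the plan supports. The primary analysis is the baseline-adjusted model; the unadjusted t-test is a secondary analysis. On the plan's own inputs the adjusted model has about 89% power for a difference of 4 and about 98% for 5, both above the synopsis figures. Even the disputed 81% is no lower than the synopsis 80%. This stands: the adjusted figures are conservative if the 35% is right, and the point is about documentation.

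A second reply is that the synopsis is a calculation at the number randomized, with section 9.1 disclosing the loss. That explains where the 95% came from. But the synopsis does not say that its figures are before loss, and under the plan patients without a follow-up score are not analysed. Enrolment may exceed 1,200, but both statements are computed at 1,200.

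A third reply is that the simulation may have used other settings. The sentences giving the adjusted powers do not repeat the SD or the analysed number, and about 370 evaluable per arm or an SD of about 27 comes close to both figures. This is fair as to cause: a low R² is not the only candidate. However, 370 of 600 per arm means about 38% loss against the stated 20%, and 27 is not the stated SD of 24. Each of these explanations therefore confirms that the section, as written, is inconsistent with itself. A correlation of 0.35 and a change-score analysis are also only near matches: each misses one of the two figures by slightly more than 2 points, and section 9.1 describes no change-score analysis.

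**Conclusion.** The concern holds in both parts. The synopsis overstates unadjusted power relative to section 9.1 by about 5 points for a difference of 5 and 7 points for a difference of 4, because it leaves out the planned loss. The adjusted powers in section 9.1 are 12 and 8 points below what its SD, loss and explained variance give.

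The documents do not show whether the 35%, the 55% and 81%, or an unreported simulation setting is at fault. The calculation rests on the inferred two-sided 5% level, equal arms, equal loss in both arms, and no effect of clinician clustering. It does not show the trial to be underpowered. The point should be fixed because the stated powers are wrong as written and the correction is cheap.

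**What to change.** 1. **Synopsis.** Restate as: 1,200 randomized, 20% loss, 960 evaluable, about 90% power for a difference of 5 and 73% for 4, unadjusted, two-sided 5%. The sponsor should confirm the alpha.

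2. **Section 9.1.** Check the simulation settings and re-run it under the planned baseline-adjusted model with 20% loss. If R² = 0.35 is right and the other stated inputs stand, restate the power as about 67% for a difference of 3 and 89% for 4. If the simulation used a lower R², a correlation of 0.35, a change score, a smaller analysed number or a larger SD, correct the assumption or the model description to match and keep the lower powers.

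3. **Reporting.** Give SD, R², loss, alpha, the analysed number per arm and the number of simulated trials beside the figures.

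The cost is one sentence in the synopsis, one or two in section 9.1, and a re-run of the simulation. No patients are added and the analysis does not change. The synopsis figures become slightly less favourable.

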6.5 KCCQ-12 Assessment at Trial Completion

This study will compare KCCQ-12 across trial arms at least one year after randomization. All patients with clinic visits between 12-15 months after their initial visit will be assigned the KCCQ-12. The data will be collected similar to the manner described above. Patients will be messaged regarding KCCQ-12 completion one week before their clinic visit. Patients who do not complete the

KCCQ-12 will be able to complete the survey in clinic during the check-in process. Patients who do not complete the survey within 15 months (either due to not having a clinic visit between 12-15 months or not completing the survey in clinic) will be contacted via telephone to complete the survey. Among patients without clinic visits, we will ask additional questions regarding their medications and other heart failure therapies.

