Multiple sensitivity analyses to account for missing data will be conducted. First, potential assumptions around mortality will be explored. The primary analysis assumes the collection of KCCQ-12 data is independent of mortality over a 1-year follow-up. If KCCQ-12 assessment is associated with a reduction in mortality, the primary analysis will underestimate the effect of KCCQ assessment on health status. If KCCQ-12 assessment is associated with increased mortality, it will overestimate the effect of KCCQ assessment. In a secondary analysis, a KCCQ-12 score of 0 will be used for all patients who die during follow-up. This secondary analysis will test if the primary findings are consistent after placing a negative weight on mortality. Second, sensitivity analyses will account for living patients with missing data. This is important given loss to follow-up may be differential between treatment arms. This will be addressed with two different imputation techniques. The first will predict follow-up KCCQ-12 score using observed patient characteristics (including baseline KCCQ) via multiple imputation. This assumes the data is missing at random. The second approach conservatively assumes patients with missing data have worse outcomes by using the minimum observed KCCQ-12 value in the trial. These sensitivity analyses will assess the robustness of the findings.

As secondary analyses, we will compare domain scores (physical limitation, social limitation, quality of life) and the clinical summary score across arms. For these models, we will adjust for baseline domain score and include random intercepts for the treating clinician.

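### Giving missing patients in both arms the same minimum score is pessimistic for each patient, but not guaranteed to be conservative for the between-arm comparison.

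*Combined protocol and SAP*

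**What the plan says.** Section 9.1 limits the primary analysis to patients with a follow-up score. Its sensitivity analyses treat deaths separately, with a score of 0. Living patients with missing scores are handled in two ways.

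- Multiple imputation from observed characteristics including baseline KCCQ, of which the plan says: "This assumes the data is missing at random".
- A single floor: "The second approach conservatively assumes patients with missing data have worse outcomes by using the minimum observed KCCQ-12 value in the trial".

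The stated reason for these two analyses is: "This is important given loss to follow-up may be differential between treatment arms". Their stated use is: "These sensitivity analyses will assess the robustness of the findings". No analysis makes a different assumption by arm, and section 9.1 does not commit to reporting living non-response by arm.

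On final data collection, section 6.5 states: "All patients with clinic visits between 12-15 months after their initial visit will be assigned the KCCQ-12". It describes collection as similar to the earlier procedures. Those were not identical: section 6.3 sends usual care to a REDCap survey and the KCCQ arm to MyHealth.

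**The concern.** The finding whose robustness is to be checked is a difference between arms, so a reader will naturally carry the word conservative over to that difference. A common floor does not earn it there. It replaces the unknown scores of missing patients by one value in both arms, so the arm with more missing patients is pulled down further. The plan gives possible differential loss as the reason for these analyses, and under differential loss the direction of the floor's effect is no longer fixed.

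This matters because the floor is the only planned check for living patients that does not assume missing at random. If a positive primary result survives it, that will be cited as support. If the floor cannot fail in the situation at hand, surviving it carries little information. Conversely, greater loss in the KCCQ arm could nearly erase a real benefit and make a sound result look fragile.

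**Working it through.** **Inputs from the documents.** 1,200 randomized 1:1 (600 per arm), 20% loss, usual-care mean 67, KCCQ mean 72 in the powered scenario, SD 24, baseline explaining 35% of variance.

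**Assumptions.** Two-sided alpha 0.05 (not stated in the documents). Floor 0 to 20 (the minimum is unknown in advance). All loss is living non-response. Missingness is unrelated to outcome unless stated. The loss by arm is illustrative.

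**Check of the plan's own figures.** With 480 per arm, SE = 24 × √(2/480) = 1.549. Unadjusted power for differences of 6, 5 and 4 is 97.2%, 89.8% and 73.3%; the plan states 97%, 90% and 73%. The inputs and alpha are therefore consistent with the plan.

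**Bias formula.** Let pT and pC be living non-response in the KCCQ and usual care arms, muT and muC the means the missing patients would have had, and m the floor. Relative to the effect with complete data, the floor adds

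bias = pC(muC − m) − pT(muT − m).

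**No true effect, 18% KCCQ / 22% usual care.**
- Floor 0: 0.22 × 67 − 0.18 × 67 = 2.68 points. Floor 20: 0.04 × 47 = 1.88 points.
- Arm variance = (1 − p) × 24² + p(1 − p)(67 − m)². At floor 0 this is 1134.9 and 1219.6, so SE = √(2354.5/600) = 1.98. At floor 20, SE = 1.65.
- Rejection in the floor analysis alone, unadjusted: 27% and 21%, almost all favouring KCCQ.
- At 20/20% the bias is zero and rejection is 5%.

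**True difference 5 (72 versus 67), floor 0 and floor 20.**

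| Missing, KCCQ / usual care | Floor estimate |
|---|---|
| 17.5 / 22.5% | 7.47 and 6.47 |
| 20 / 20% | 4.00 and 4.00 |
| 22.5 / 17.5% | 0.53 and 1.53 |

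For example, 0.825 × 72 − 0.775 × 67 = 7.47 at floor 0.

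**Break-even.** Setting the bias to zero at average loss 20% and difference D gives pC − pT = 0.4 × D / (134 + D − 2m). For D = 4 this is 1.16 points (floor 0) to 1.63 (floor 20); for D = 5, 1.44 to 2.02. A larger usual-care excess inflates the benefit; a smaller one still shrinks it.

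**When missing patients differ between arms.** The sign can go either way.
- Usual-care excess acting against KCCQ: pC 22%, muC − m = 45; pT 18%, muT − m = 60. Bias = 9.9 − 10.8 = −0.9.
- Equal loss hiding harm: 20/20%, no effect among completers, missing KCCQ patients 10 points worse than missing usual-care patients. The complete-data effect is −0.2 × 10 = −2.0, while the floor gives 0. A simulation with scores clipped to 0–100 gave −1.87 and about 0.

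**Primary and floor analyses together, no true effect.** Simulation with 4,000 trials per scenario, 600 per arm, baseline-adjusted, without the clinician intercept:
- Both favour KCCQ significantly in 2.0 to 2.2% of trials at 17.5/22.5%, 1.6 to 2.0% at 18/22%, and 0.7 to 0.8% at 20/20%.
- Given a false-positive primary result, the floor agrees in roughly 90% of trials at 17.5/22.5%. At equal loss the figure is about 25 to 37%, a range that includes a second, smaller simulation.

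**The case against.** **The sentence is not wrong as written.** The adverb qualifies an assumption about patients, and the plan never says which way the arm difference moves. That stands. The difficulty is what a reader will infer, given the stated purpose of testing robustness.

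**The rejection rates overstate the danger.** A reader might infer that the floor produces a false claim of benefit in a fifth or more of trials. It does not. Those rates describe the floor analysis alone. Most of its favourable rejections under no effect occur when the primary result is not significant, so the two analyses visibly disagree, and multiple imputation is there as well. Joint false support stays near 2%. What survives is narrower: under a systematic usual-care excess, the floor no longer screens out false-positive primary results.

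**General rules about direction fail.** It is tempting to say that any usual-care excess favours KCCQ, or that equal loss is always safe. The two counterexamples in the working contradict both. The first needs equal means among missing patients; the second needs missing KCCQ patients to do no worse than missing usual-care patients.

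**The loss difference is assumed.** This also stands. Chance alone rarely gives a large gap: at equal 20% loss the SE of the gap is √(2 × 0.2 × 0.8/600) = 0.0231, so a usual-care excess of 5 points or more arises in about 1.5% of trials. Chance gaps are already in the SE, so the raised rejection rates need systematic differential loss. Survey contact during follow-up does differ by arm (sections 6.4.2 for each arm), which makes such loss plausible. It does not show that usual care would lose more.

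**Conclusion.** The concern holds in limited form: the floor is pessimistic for each missing patient but not guaranteed to be conservative for the treatment comparison.

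If missing patients have equal means in both arms, a systematic excess of usual-care loss biases towards KCCQ and an excess in the KCCQ arm biases against it. Equal loss shrinks a benefit that the missing patients share. If missing KCCQ patients are truly worse off than missing usual-care patients, even equal loss can hide harm.

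Under the stated assumptions, a 4-point gap in loss moves a null effect by 1.9 to 2.7 points. A 5-point gap turns a true 5 into 6.5 to 7.5, or 0.5 to 1.5 if reversed.

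The documents do not support reading this as a flaw in the primary analysis, as a prediction that usual care will lose more patients, or as a high risk that both analyses are falsely positive. Nor do they establish identical final collection in the two arms, since section 6.5 says only that it is similar to the earlier routes. Severity is low to moderate: one sensitivity analysis is affected, to an extent that depends on a loss difference the documents do not quantify.

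**What to change.** 1. In section 9.1, delete the word conservatively or limit it to the patient-level score. Keep the floor, if wanted, as an extreme scenario.
2. Add delta-adjusted multiple imputation on top of the imputation already planned. Shift imputed scores in the KCCQ arm only, in the usual care arm only, and in both. Prespecify a range that the investigators justify and that extends to the tipping point, and report that point.
3. Report living non-response and deaths by arm beside these results, so that the direction of the floor's effect can be judged.

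For the scale of the range: with 20% missing and 35% of variance explained, the adjusted SE is 24 × √0.65 × √(2/480) = 1.25 (the complete-case SE, used as an approximation). A KCCQ-only shift removes significance at (estimate − 1.96 × 1.249)/0.2, which is 7.8 points for an estimate of 4 and 12.8 for an estimate of 5. It removes the estimate itself at 4/0.2 = 20 and 5/0.2 = 25 points.

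The cost is a change of SAP wording and a little more analysis work. No new data are needed.
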